7.4 PARTICIPANT RECRUITMENT AND INFORMED CONSENT

Participants will be recruited in the United States through web media (e.g. Facebook, Google Ads) [REDACTED]. Potential participants will be asked to provide contact information (first name, phone number, email address), and answer questions on demographics (gender, age, employment status, location via city and state, race/ethnicity), smartphone ownership, and smoking attitudes and behavior (Stage of Change and CPD) using the Online Screening Form [REDACTED]. Study staff will review each potential participant's responses to the eligibility questions.

Online screening form responses will be reviewed by study staff. Using non-proportional quota sampling, potential participants will be called on a first-come-first-served basis, as possible, with the aim to enroll 40-60% males, 40-60% females, no more than 50% of participants from any decade-spanning age group (ex. 30-39 years of age, etc.), no more than 70% of participants in the non-Hispanic white race category and up to 20% unemployed. The goals of these non-proportional quota sampling ranges are to ensure

representation among males, racial/ethnic minorities, age groups, and individuals with varying socioeconomic status. Regarding the non-proportional quota sampling for employment, at the time of protocol design (March and April, 2021) the unemployment rate in the U.S. was 6.0%.[24] Acknowledging a higher unemployment rate among people who smoke [25-28], and the desire to include individuals who either do not receive payment for their work or are not pursuing employment (stay-at-home parents, caretakers, students, retired individuals) we will enroll up to 20% of participants who do not currently have employment for which they are compensated.

During the screening phone call, potential participants will be asked questions to confirm study eligibility [REDACTED]. During this call, study personnel will inform the potential participant of the study details and will answer any questions.

Potential participants will then determine if they would like to proceed. If they would like to proceed, study staff will arrange for a brief (1-2 minute) videocall with the potential participant using the HIPAA-compliant study videoconference platform to confirm capability on the participant's behalf. This call should be completed prior to randomization. Study personnel will email the potential participant an electronic HIPAA Authorization form and an electronic Informed Consent Form (ICF) [REDACTED]. The potential participant will have ample time to read these forms and the opportunity to ask questions. The participant will sign the electronic HIPAA Authorization and ICF before participating in this study. The ICF will seek documented confirmation of potential study participant's readiness to quit smoking in the next 30 days. Once signing the ICF, the participant will be given a unique identifier [REDACTED] to protect participant privacy.

7.5 PARTICIPANT RANDOMIZATION, STRATIFICATION AND ENROLLMENT

After signing the ICF, the participant will complete an online Baseline Questionnaire. Based on responses to the questionnaire, participants will be randomly assigned in a computer-generated 1:1 manner to either Pivot or QuitGuide using randomly permuted blocks of size 2 and 4, stratified by daily smoking frequency (≤ 14 vs ≥ 15 cigarettes per day), employment status (full-time or part-time employment vs unemployed), race/ethnicity (minority race/ethnicity vs non-Hispanic White), and expected difficulty staying quit (scale 1-10; self-reported score of ≤ 5 vs. ≥ 6). After randomization, participants will be emailed the link to access their assigned group. In both groups, participants will be able to access their assigned study app from the moment of randomization and beyond (ie, after the end of the 2-year study period).

Participants will be considered enrolled after completing the following 3 tasks: electronically signing the informed consent form, completing the Baseline Questionnaire and reporting the date they first logged in to their assigned app. If participants do not complete all three criteria, they may be removed from the study.

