	
 ○ Number of times app opened ○ Number of days in which app was opened ○ Number of weeks in which app was opened ● Participant changes in self-efficacy ● Participant changes in self-reported health and wellbeing ● Self-reported nicotine replacement therapy (NRT) use ● Use of other smoking cessation tools (apps, counseling, medications, etc.) ● Adverse events
Potential Subjects	Up to 180 adult participants who are daily cigarette smokers and are planning to quit smoking in the next 30 days.
Inclusion Criteria	
 ● 21+ years of age ● Current daily cigarette smokers (at least 5 cigarettes per day) for the past 12 months ● Plans to quit smoking in the next 30 days ● Resident of the United States ● Able to read and comprehend English ● Owns and uses a smartphone compatible with the study app (iPhone 5 and above with operating system iOS 12 and above, or, Android 7.0 and above with operating system Android 7.0 and above) ● Has daily internet access on smartphone ● Comfortable downloading and using smartphone apps ● Willing to sign the Informed Consent Form
Exclusion Criteria	
 ● Pregnancy (self-reported) ● Health contraindications to NRT use (irregular heartbeat, high blood pressure not controlled with medication, heart attack or stroke in last 2 months, pregnant or breast feeding, skin allergies to adhesive tape or serious skin problems, stomach ulcers, history of seizures) ● Using other smoking cessation support, including apps and/or actively taking medication to quit smoking ● Daily marijuana use ● Residence with another person who is a participant in this study ● Immediate family member is a participant in this study ● Failure to provide contact or collateral information, failure to verify email address, and/or failure to demonstrate videoconference capability ● Participation in a previous study sponsored by Pivot Health Technologies Inc. (formerly Carrot Inc.)
Recruitment	Eligible subjects will be identified via web media (e.g., Facebook, Google ads).
Study Session	This is an open-label, two-arm, parallel-group, non-crossover, single-center pilot randomized controlled trial conducted with IRB approval enrolling up to

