7.11 STUDY PERSONNEL

The study team members will be trained by reading the study protocol. The study team members will have full training on the QuitGuide and Pivot apps, and operation of the Pivot Breath Sensor. Study team members will also have documentation of HIPAA / HITECH Security Awareness training and NIH Protecting Human Research Participants training.

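### Small block sizes are printed in the protocol that study staff train on, in an open-label trial with no stated allocation concealment, so assignments are partly predictable and selection bias is an avoidable risk

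*Combined protocol and SAP*

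**What the plan says.** - Section 7.5, on the scheme: a computer allocates 1:1 from the baseline answers, "using randomly permuted blocks of size 2 and 4, stratified by daily smoking frequency". The other three factors are employment, race/ethnicity and a self-rating given as "expected difficulty staying quit (scale 1-10; self-reported score of ≤ 5 vs. ≥ 6". Four binary factors make 16 strata.
- Section 7.5, on timing: "After signing the ICF, the participant will complete an online Baseline Questionnaire". Allocation follows that questionnaire.
- Section 7.4: before anyone is called, staff review a form covering employment status, race/ethnicity and "smoking attitudes and behavior (Stage of Change and CPD) using the Online Screening Form". Expected difficulty staying quit is not among the items listed. Within recruitment quotas, "potential participants will be called on a first-come-first-served basis, as possible".
- Section 7.11: "The study team members will be trained by reading the study protocol".
- Synopsis, Study Session: "This is an open-label, two-arm, parallel-group, non-crossover, single-center pilot randomized controlled trial".

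The text of 7.5 carries no redaction. It does not say who holds the sequence, whether it is concealed, or whether recruiting staff can see earlier assignments.

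**The concern.** Permuted blocks protect against selection bias only while those who recruit cannot work out what comes next. Here the sizes are small and are printed in the staff's training document, and assignments are open once made (for example, only the Pivot arm is mailed a sensor at the start). Before calling, staff already hold three of the four stratification factors.

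Several steps before allocation involve staff: the order of calls, the eligibility call and the videoconference check. Computer allocation after consent does not remove discretion over those steps. The primary outcome, app opens, and the abstinence outcomes plausibly depend on motivation. If keener candidates were called when a Pivot slot looked likely, the comparison would tilt towards Pivot, and adjusting for the stratification factors would not remove the tilt.

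**Working it through.** **1. The plan's own figure.** Section 7.7 assumes 25 (SD 25) against 15 (SD 19) opens. The common SD is √[(25² + 19²)/2] = 22.2. A two-sided two-sample t-test at 0.05 with power 0.80 for a difference of 10 needs 156.72 participants in total, which reproduces the stated 156.7. This figure is not in dispute; it supplies the SD used in step 5.

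**2. Predictability when the stratum and its history are known.** The strategy is to guess whichever arm is behind in the stratum. Expected correct guesses per block, by enumeration:
- size 2: 1.5 of 2 (75.0%)
- size 4: 2.833 of 4 (70.8%)
- equal mix: (1.5 + 2.833)/6 = 72.2%, against 50% by chance

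A next assignment is certain when a block of 4 opens with two of the same arm. This happens in 1/3 of such blocks and fixes the last two places, so the share is (1/3 × 2)/6 = 11.1%.

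**3. The trial's size and strata.** I simulated 180 participants in 16 strata with an optimal guesser who knows the block sizes and past assignments. Assumptions not in the documents: equal chance of each block size; 50% at 15 or more cigarettes per day; 20% unemployed; 35% minority; and 12-24% scoring 6 or more on expected difficulty, with 50% as a sensitivity case. The low range is suggested by the baseline means of 3.7 and 3.1 in the Background, where a rise is reported as less difficulty.

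| | Blocks 2/4 | Blocks 4/6/8 |
|---|---|---|
| Correct, four factors known | 71% | 66% |
| Certain, four factors known | 10% | 2% |
| Correct, three known (12-24% mix) | 68-70% | 64-66% |
| At least 80% sure, three known (12-24% mix) | about 23-39% | 8-13% |
| Mean arm imbalance of 180 | about 2.6 | about 3.4 |

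With 50% scoring 6 or more, the three-factor figure for blocks 2/4 is about 65%. Hence the range of 65-70% at the time of the call.

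**4. Delay between call and allocation.** The videocall, the consent forms and the Baseline Questionnaire come in between, and others may be randomized meanwhile. The documents do not give the delay. With three factors known, the 12-24% mix and blocks 2/4:
- nobody in between: 68-70% correct
- 3 others: 63-64%
- 5 others: 61%
- 10 others: about 57%, when blocks 4/6/8 give 58%

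**5. What this could do to the primary comparison.** Suppose steering shifts a candidate's expected opens by *s* up or down according to the guess, for every candidate, and guesses are right with probability *p*. The arms then differ by 2*s*(2*p* − 1) with no true effect. With 15% attrition, 180 × 0.85/2 gives about 76 per arm, so SE = 22.2 × √(2/76) = 3.60. The shift *s* is an assumption; the documents give none.

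| *s* | *p* | Bias (opens) | Type I error |
|---|---|---|---|
| 2.5 | 70% | 2 × 2.5 × 0.4 = 2.0 | about 9% |
| 2.5 | 60% | 2 × 2.5 × 0.2 = 1.0 | about 6% |
| 1 | 70% | 0.8 | about 6% |
| 5 | 70% | 4.0 | about 20% |

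If only a quarter of candidates are steered at *s* = 2.5 and *p* = 70%, the bias is 0.25 × 2.0 = 0.5 opens and type I error stays at about 5%.

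**The case against.** The strongest reply has five parts.

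- **The guess is made too early.** At the call the fourth factor is unknown and allocation is still several steps away. This stands: it lowers accuracy from 71% to 65-70%, and further with each person randomized in between. Prediction stays above chance in every case examined.
- **Guessing needs a running record by stratum.** That includes earlier participants' difficulty scores. The documents neither say that recruiting staff see this nor rule it out. The screening-call questions and the data-management procedure are redacted, so access controls may exist there. The point is therefore limited to what the readable text of 7.5 and 7.11 discloses and leaves unsaid.
- **Discretion is limited.** Calling is broadly in order of arrival, under quotas, and every eligible candidate must already plan to quit within 30 days, so Stage of Change separates candidates less than it might. This reduces the scope for steering but does not remove it.
- **Larger blocks help little.** This stands for overall accuracy (71% to 66%, and no gain at a delay of 10). They do cut certain guesses from about 10% to 2%.
- **It may be too late.** The latest revision adds a 104-week visit, so enrolment may be over. That is an inference; if it is right, only the sensitivity check remains.

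A reader might infer that staff could usually tell the next assignment before picking up the phone, or that the trial's type I error is 9% or more. The documents support neither. The first needs the full stratum and no delay; the second also needs every candidate to be steered by an assumed amount.

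**Conclusion.** The concern holds as an avoidable weakness in allocation concealment. Small block sizes are disclosed to staff in an open-label trial, and the readable text states no safeguard. Predictability is about 71% at most, 65-70% at the time of the call with no delay, and about 64% to 57% with 3 to 10 others randomized in between. All these figures assume tracking by stratum and the stated stratum mixes.

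The bias of 2.0 opens, against a planned difference of 10, is an upper bound for an assumed shift of 2.5. It is 1.0 at 60% correct guessing and smaller if only some candidates are steered. Nothing in the documents shows that steering took place. The change is worth making because it costs almost nothing and because, as written, the plan has no answer to a question about concealment.

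**What to change.** 1. In 7.5, replace the printed sizes with wording such as: *randomly varying block sizes not disclosed to study staff*. Hold the list and the sizes in a restricted randomization file.
2. State in 7.5 that staff who screen and call candidates cannot see the list or the running assignments by stratum. Items 1 and 2 are the main remedy.
3. Drop the size-2 block, for example by drawing from 4, 6 and 8. This mainly removes certain guesses.
4. If enrolment is complete, items 1 to 3 no longer help. Add a Berger-Exner sensitivity check instead: regress the outcome on the predicted probability of Pivot, adjusting for arm, using the existing allocation list. A null result would be reassuring but would not exclude selection bias.

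Cost: a new list and a few sentences. Mean arm imbalance rises by about one participant or less in 180 (about 2.6 to 3.4). The sample size is unaffected and no new data are needed.

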- Number of quit attempts at 4, 12, 26, 52, and 104 weeks (defined as answering ≥ 1 to the following question: “Since you began the study, how many times have you tried to quit smoking where you've gone at least 1 day without smoking a cigarette, even a single puff?”).
- User satisfaction with the smoking cessation program (set-up and getting started with program, recommend to friend, program design, program was useful for quitting, program helped me quit, program helped me stay quit) at 2, 3, 4, 5, 12, 26, 52 and 104 weeks
- Engagement with program, collected weekly during the first 12 weeks after enrollment:
 - Number of times app opened (self-report)
 - Number of days in which app was opened (self-report)
 - Number of weeks in which app was opened (self-report)
- Participant changes in self-efficacy at 6, 12, 26 and 52 weeks
- Participant changes in self-reported health and wellbeing at 26 and 104 weeks
- Self-reported NRT use at 4, 8, 12, 26, 52 and 104 weeks
- Use of other smoking cessation tools (apps, counseling, non-study medications, etc.) at 12, 26, 52, and 104 weeks
- Alcohol use behavior at 12, 26 and 52 weeks (Alcohol Use Disorders Identification Test-Concise or AUDIT-C screening questionnaire, 3 items) [18-20]
- Presence of depressive symptoms screening at 12, 26, and 52 weeks (Center for Epidemiological Studies Depression Scale or CES-D screening questionnaire, 10 items) [11,21-23]
- Living and social environment relating to cigarette smoking at 12, 26 and 52 weeks (live with other adults who smoke, live with romantic partner who smokes, number of close friends who smoke)
- Adverse events at 26, 52 weeks

Eligibility Criteria

The study population comprises current smokers, 21 years of age and above, who own and

regularly use a smartphone and are ready to quit smoking in the next 30 days.

Inclusion Criteria

- 21+ years of age
- Current daily cigarette smokers (at least 5 cigarettes per day) for the past 12 months
- Plans to quit smoking in the next 30 days
- Resident of the United States
- Able to read and comprehend English
- Owns and uses a smartphone compatible with the study app (iPhone 5 and above with operating system iOS 12 and above, or, Android 7.0 and above with operating system Android 7.0 and above)
- Has daily internet access on smartphone
- Comfortable downloading and using smartphone apps
- Willing to sign the Informed Consent Form

Exclusion Criteria

- Pregnancy (self-reported)

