8.2 REGISTRATION

After electronically signing the Informed Consent Form, the participant will complete the online Baseline Questionnaire. After completing the Baseline Questionnaire, participants will undergo computer-generated randomization to either the intervention or control study group, as described in section 7.5 *Participant Randomization, Stratification and Enrollment*. Participants are then emailed a link for their assigned app. Upon opening the link, participants will register in their assigned app, providing baseline information on their smoking behavior. While participants are encouraged to select a quit date in their app that occurs within 30 days of enrollment, this is not required for participation.

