8.3 ACTIVE PROGRAM USE

The participant will initiate use of their assigned program. To be considered enrolled, one must: sign the electronic informed consent form, complete the Baseline Questionnaire, and provide the date they first logged in to their assigned app. Participants may receive up to two text or email messages during the first week of the study reminding them to go into their study app and confirm they have done so. There is no pre-determined time limit on how long a participant can actively engage in their app, although it is expected most participants will complete engagement by 6 months from enrollment. For individuals enrolled in the intervention arm, coaching is available for up to 12 months from enrollment. In both arms, participants may order up to 12 weeks of NRT, in two-week increments over the first 12 months of the study. Pivot is designed to be a 12-month program. There is one possible biovalidation videocall visit at 12 weeks during this portion of the study and weekly online questionnaires at the end of weeks 1 through 12.

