8.6 REMINDERS

Over the first 12 weeks of the study, participants will receive an email or text reminder to engage with their assigned program every other week (for a total of 6 reminders). These reminders will be sent out during weeks 1, 3, 5, 7, 9 and 11. Two of these communications will remind participants of the availability of NRT. During the first week of the study, participants may receive up to an additional two text or email messages reminding them to log into their study app and confirm they have done so.

Participants will receive periodic reminders from study staff to complete their questionnaires via email, text or phone, as needed. All participants will receive all questionnaires, regardless of completion of previous questionnaires. [REDACTED]
[REDACTED]
[REDACTED]

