10. TECHNICAL APPROACH AND STUDY DESIGN

10.1 ACCEPTANCE CRITERIA

Data will be accepted if the participant meets eligibility criteria, and completes the electronic informed consent form, the Baseline Questionnaire and reports a date they first opened their assigned study app.

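### The plan permits, but does not require, a primary comparison of app opens limited to randomised people who reported a first login or open

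*Combined protocol and SAP*

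**What the plan says.** Order of events. Section 8.2 states: "After completing the Baseline Questionnaire, participants will undergo computer-generated randomization". Sections 7.5 and 8.2 then have the app link emailed, so the first login always follows assignment.

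Enrolment. Sections 7.5 and 8.3 list three tasks: consent, the Baseline Questionnaire, and, as 8.3 puts it, to "provide the date they first logged in to their assigned app". The first two precede randomisation, so the login report is the only task that can remove someone already randomised. Section 7.5 supplies the consequence: "If participants do not complete all three criteria, they may be removed from the study".

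Data acceptance. Section 10.1 accepts data from an eligible participant who has completed consent and the questionnaire and "reports a date they first opened their assigned study app". It does not say what happens to other data.

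Analysis. The primary outcome (7.3) is total app opens, Pivot versus QuitGuide, at 12 weeks. Section 11.2 names no analysis population. Intention to treat appears in the abbreviation list and, in the visible text, otherwise only for an earlier cohort study.

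Time origin. Under 7.5, "participants will be able to access their assigned study app from the moment of randomization", while the secondary engagement outcome in 7.3 reads "Engagement with program, collected weekly during the first 12 weeks after enrollment". The primary outcome says only 12 weeks.

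**The concern.** A person who never opens the app has zero opens, the lowest possible value of the primary outcome. A filter that requires at least one reported open takes those zeros out of the comparison, and the resulting groups are no longer protected by randomisation. Removal is discretionary, the trial is open-label (synopsis), and the visible text gives neither a deadline nor a rule for deciding, so nothing stated keeps the decision independent of arm. Section 7.7 powers the trial on exactly this between-arm comparison, so its pilot status does not set the point aside. Without a defined population and per-arm counts, a reader of the results could not tell a negligible bias from a material one.

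**Working it through.** **Inputs.** From 7.7: mean (SD) 25 (25) for Pivot and 15 (19) for QuitGuide, power 0.80, alpha 0.05. From 7.5: 1:1 allocation. The share p who never open the app is not documented in either arm, so every p below is an assumption.

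**The plan's own figure.** Pooled SD = √((25² + 19²)/2) = 22.20 and d = 10/22.20 = 0.450. A two-sided two-sample t-test needs 78.36 per arm, or 156.7 in total, rounded to 79 per arm (158). This reproduces 7.7. Welch power at 79 per arm is 0.803.

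**Reading 1: the planning values include zeros.** The true difference is 10. Among openers, mean = m/(1−p), E[X²] = (SD² + m²)/(1−p), and n = 79(1−p).

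| Pivot/QuitGuide never-openers | Openers-only means | Difference |
|---|---|---|
| 1%/3% | 25.25 − 15.46 | 9.8 |
| 3%/1% | 25.77 − 15.15 | 10.6 |
| 5%/5% | 26.32 − 15.79 | 10.5 |
| 5%/15% | 26.32 − 17.65 | 8.7 |
| 15%/5% | 29.41 − 15.79 | 13.6 |

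Openers-only power is 0.82 at 5%/5%, 0.64 at 5%/15% and 0.95 at 15%/5%. The shift is upward when 25·p/(1−p) for Pivot exceeds 15·p/(1−p) for QuitGuide, and downward otherwise.

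**No true difference (both arms 15 (19), zeros included).** Balanced non-start creates no spurious difference, and the false-positive rate stays at 0.05. At 1%/3% the spurious gap is 15/0.97 − 15/0.99 = 0.31 opens and the rate is 0.051. At 5%/15% the gap is 15/0.85 − 15/0.95 = 1.86 opens and the rate is 0.088.

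**Reading 2: the planning values describe openers only.** The all-randomised mean is m(1−p). The difference becomes 23.75 − 14.25 = 9.5 at 5%/5%, 23.75 − 12.75 = 11.0 at 5%/15%, and 21.25 − 14.25 = 7.0 at 15%/5%. With 79 openers per arm and the never-openers added back, power is 0.79, 0.91 and 0.56. Section 7.7 does not say which reading applies.

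**Who is counted in the 180.** If 7.7 means 180 enrolled as 7.5 defines it, the number randomised would be 180/0.98 ≈ 184 at 2% non-start, 180/0.95 ≈ 189 at 5%, and 180/0.90 = 200 at 10%. About 4, 9 or 20 randomised people could then fall outside the analysis.

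**Limit of the model.** These rows treat everyone left out as a true zero. The documents' criterion is a *reported* login, so some of those left out may have opened the app and not said so. The rows do not describe that group.

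**The case against.** The strongest reply is that exclusion is not a rule. Section 7.5 says such people may be removed, and 10.1 says data are accepted if the date is given, not only if. Section 8.6 sends every questionnaire to all participants whatever they completed before, although that does not settle who remains a participant. A reader might infer that the plan requires an openers-only analysis; the wording does not support that.

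Non-start may also be rare. Eligibility requires comfort with apps, daily smartphone internet and a plan to quit within 30 days (7.3). A screening call and a videocall precede randomisation (7.4). Week 1 allows up to two messages "reminding them to go into their study app and confirm they have done so" (8.3, repeated in 8.6). At gaps such as 1%/3% the effect is very small. All of this stands, but the documents give no rate.

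A reader might also infer that the filter favours Pivot. The criterion is worded alike for both arms, and the illustration moves in either direction, so that inference is unsupported.

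Finally, the schedule of activities (8.8), part of 8.6 and the consent form are redacted, and an operational cut-off could be there. The absence of a deadline is therefore a statement about the visible text only.

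What remains is that stated rules allow randomised people to be dropped on part of the outcome, and nothing visible overrides them.

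**Conclusion.** The point holds as a structural one and should be fixed: the plan permits a primary comparison restricted by a post-randomisation event that is itself an instance of the outcome. Confidence is high on the structure and does not extend to size or direction. The numerical illustration rests on assumed never-opener rates, on the planning values including zeros, and on a two-sided Welch t-test, which 11.2 does not specify. On those assumptions the effect is a few tenths of an open when non-start is 1% to 3%. It reaches about −1.3 or +3.6 opens, against a planned difference of 10, when the arms differ by ten percentage points.

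It would go too far to call the mixed time origins a proven error in the primary outcome. The count from enrolment is attached to the secondary engagement measure, and no resulting bias can be quantified. The origin for the primary outcome simply needs stating.

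**What to change.** - **11.2:** make all randomised participants, analysed as assigned, the primary population. Keep openers-only as a sensitivity analysis.
- **7.5 and 10.1:** remove the reported first login as a condition for staying in the study or for data being analysed. Consent, eligibility and the Baseline Questionnaire precede randomisation and can stay.
- **Outcome rule:** use the same self-report source and the same zero rule in both arms, because 11.1 says QuitGuide yields no automated data. Score 0 opens when the participant reports no use.
- **Non-reporters:** treat them as missing, with sensitivity analyses that include scoring them 0. State plainly that silent never-openers enter as zeros only in that sensitivity analysis, so the primary analysis will not recover them fully.
- **Reporting:** give randomised, never-opener and non-reporter counts by arm.
- **7.7:** say whether 180 means randomised or enrolled.
- **Time origin:** it need not be moved, and moving it to randomisation could mean rescheduling the weekly questionnaires. State which origin applies to the primary outcome and how the 12-week window is set for people who never report a login.

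The cost is wording changes, some missing-data analysis and possibly slightly lower reported mean opens. Each retained non-starter could cost up to $365 + 4 × $50 = $565 in payments (7.6), plus any study NRT or breath sensor supplied. If the study is already under way, which the revision history suggests but does not state, data not collected from people already removed may not be recoverable, but those people can still be counted by arm.
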